6.6. Multicenter Studies

Data will be pooled across all clinical sites. Center effects are not anticipated because the sites are using standardized procedures for vaccination and assessment of solicited and unsolicited adverse events, and the study relies on central laboratories for the assessment of immunogenicity endpoints.

6.7. Multiple Comparisons/Multiplicity

There are no adjustments planned for multiple comparisons.

7. STUDY SUBJECTS

7.1. Disposition of Subjects

[Table 14](#) will present a summary of the reasons that subjects were screened but not enrolled.

The composition of analysis populations, including reasons for subject exclusion, by treatment arm, is presented in [Table 13](#).

The disposition of subjects in the study will be tabulated by treatment group ([Table 10](#), [Table 11](#) and [Table 12](#)). The table shows the total number of subjects screened, enrolled, receiving first vaccination, discontinuing treatment, receiving second vaccination, study ongoing or terminated from study follow-up and the number completing the study.

A flowchart showing the disposition of study subjects, adapted from the Consort Statement [1] will be included ([Figure 1](#), [Figure 2](#) and [Figure 3](#)). This figure will present the number of subjects screened, enrolled, lost to follow-up, and analyzed, by treatment group.

A listing of subjects who discontinued dosing or terminated from study follow-up and the reason will be included in [Listing 2](#).

7.2. Protocol Deviations

A summary of subject-specific protocol deviations will be presented by the reason for the deviation, the deviation category, and treatment group for all subjects ([Table 4](#), [Table 5](#), [Table 6](#)) as well as similar summaries for major subject-specific protocol deviations ([Table 7](#), [Table 8](#) and [Table 9](#)). All subject-specific protocol deviations and non-subject specific protocol deviations will be included in [Appendix 3](#) as data listings ([Listing 3](#) and [Listing 4](#), respectively).

8. IMMUNOGENICITY EVALUATION

8.1. Primary Immunogenicity Analysis

See Section 9 for safety analyses which are the primary endpoints of this study.

8.2. Secondary Immunogenicity Analyses

Summaries and analysis of immunogenicity data will be presented for the mITT population. If there are protocol deviations which may affect the analysis, a per-protocol (PP) analysis may also be performed. If PP population is different than mITT then the PP population will be used in the interim CSR (iCSR).

Seroconversion is defined as a 4-fold increase in antibody titer over baseline. AUC is calculated using the trapezoidal method applied to a serial dilution curve. For samples with an AUC of zero at baseline, fold-rise will be calculated by dividing post-vaccination result by the lowest reported value.

Seroconversion rates, GMFR, GMT or Williams mean of the AUC for SARS-CoV-2 (S-2P and RBD) as measured by IgG ELISA will be calculated at Days 1 (GMT only) and 57 by cohort and will be summarized graphically (log₁₀ scale). Seroconversion rates, GMFR, GMT or Williams mean of the AUC will be presented with their corresponding 95% confidence interval (CI) estimates (using Student's t-distribution) at each timepoint and overall peak GMT/AUC (starting at Table 24 and ending at Table 47 for GMT/Williams mean and starting at Table 114 and ending at Table 137 for GMFR and seroconversion summaries). Graphical displays will include reverse cumulative distribution plots (Figure 4, Figure 5, Figure 6, Figure 7, Figure 8, Figure 9, Figure 10 and Figure 11), individual titer values over time (starting at Figure 12 and ending at Figure 19), geometric mean over time (Figure 24, Figure 25, Figure 26, Figure 27, Figure 28, Figure 29, Figure 30 and Figure 31) and distributions of responses over time (starting at Figure 48 and ending at Figure 71). Note only endpoint titer values will be reported in the iCSR.

Individual immunogenicity responses are shown in Listing 8.

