8.3. Exploratory Immunogenicity Analyses

Summaries and analysis of immunogenicity data will be presented for the mITT population. If there are protocol deviations which may affect the analysis, a PP analysis may also be performed. If PP population is different than mITT then the PP population will be used in the interim CSR.

Seroconversion is defined as a 4-fold increase in antibody titer over baseline.

Seroconversion rates, GMFR, GMT or Williams mean of AUC for SARS-CoV-2 (S-2P and RBD) as measured by IgG, IgA and IgM ELISA, calculated for specified timepoints by cohort and will be summarized graphically (log₁₀ scale). Seroconversion rates, GMFR, GMT, and Williams mean of AUC will be presented with their corresponding 95% CI estimates (using Student's t-distribution) at each timepoint and overall peak GMT/AUC (starting at Table 24 and ending at Table 47 for GMT/Williams mean and starting at Table 114 and ending at Table 137 for GMFR and seroconversion summaries). AUC is calculated using the trapezoidal method applied to a serial dilution curve. For samples with an AUC of zero at baseline, fold-rise will be

calculated by dividing post-vaccination result by the lowest reported value. Graphical displays will include reverse cumulative distribution plots (Figure 4, Figure 5, Figure 6, Figure 7, Figure 8, Figure 9, Figure 10 and Figure 11), individual titer values over time (starting at Figure 12 and ending at Figure 23), geometric mean over time (Figure 24, Figure 25, Figure 26, Figure 27, Figure 28, Figure 29, Figure 30 and Figure 31) and distributions of responses over time (starting at Figure 48 and ending at Figure 71). Note only endpoint titer values will be reported in the iCSR.

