Neutralization assays using SARS-CoV-2 pseudovirus neutralization assay (PsVNA) or a wild-type SARS-CoV-2 plaque reduction neutralization test (PRNT) will be run using serial dilutions. ID₅₀ and ID₈₀ will be calculated for PsVNA data using a 5-parameter logistic regression model. ID₅₀ and ID₈₀ will be summarized by group using the geometric mean and 95% CI (using Student's t-distribution) (starting at Table 48 and ending at Table 59). Table 60, Table 61, Table 62 and Table 63 show the day 43 GM summaries of the PsVNA assay at day 43 of the 614D variant. Similarly, for PRNT data, PRNT₈₀ will be calculated using a 5-parameter logistic model. PRNT₈₀ will be summarized using a geometric mean and 95% CI (Table 64, Table 65, Table 66, Table 67, Table 68 and Table 69). Neutralization endpoints will also be displayed graphically on a log₂ or a log₁₀ scale. Similar methods will be used to summarize all additional neutralization assays performed (nanoluciferase-based live virus high throughput neutralization assay, nLuc HTNA, and 2 versions of a live virus focus-reduction neutralization test, FRNT and FRNT-mNG) (starting at Table 70 and ending at Table 95). Graphical displays for PsVNA will include individual titer values over time (Figure 20, Figure 21, Figure 22, and Figure 23), geometric mean over time (Figure 32, Figure 33, Figure 34, and Figure 35) and distributions of responses over time (starting at Figure 72 and ending at Figure 83). Graphical displays for PRNT, nLuc-HTNA, FRNT and FRNT-mNG will include geometric mean over time (starting and Figure 36 and ending at Figure 47) and distributions of responses over time (starting at Figure 84 and ending at Figure 103).

Individual immunogenicity responses are shown in Listing 8.

Spearman correlation between various binding and neutralization assays will be assessed starting at Figure 104 and ending at Figure 115.

Summaries and analysis of cellular assay data will be presented for the mITT population. If there are protocol deviations which may affect the analysis, a PP analysis may also be performed. If PP population is different than mITT, then the PP population will be used in the interim CSR.

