9. SAFETY EVALUATION

Summaries and analysis of safety data will be presented for the Safety Analysis Population.

Solicited AEs will be summarized by severity for each day post vaccination (Days 1-8) and as the maximum severity over all 8 days. Additionally, solicited AEs will be analyzed by taking the most severe response over the follow-up period, dichotomizing into a binary variable (none versus mild, moderate, or severe) and using standard techniques, such as exact confidence intervals (CI), to summarize the proportion of subjects reporting each symptom, any application site symptom, and any systemic symptom.

Unsolicited non-serious AEs will be collected from the time of first vaccination through 28 days after the last vaccination. Unsolicited AEs will be coded by MedDRA[®] for preferred term and system organ class (SOC). All SAEs, MAAEs and NOCMCs will be collected from the time of first vaccination through the end of the study (Day 394). The numbers of SAEs and MAAEs will be reported by detailed listings showing the event description, MedDRA[®] preferred term and SOC, relevant dates (vaccinations and AEs), severity, relatedness, and outcome for each event. Non-serious unsolicited AEs will be summarized as number and percentage of subjects reporting at least one event in each MedDRA[®] preferred term and SOC, cross-tabulated by severity and relationship to study product. Additionally, the proportion of subjects and exact 95% CIs of AEs in aggregate and by MedDRA[®] categories will be computed.

Clinical laboratory data will be summarized by severity and relationship for each visit, and as the maximum over all post-vaccination visits. Graphical presentations will include bar plots.

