9.3.1. Solicited Events and Symptoms

Systemic solicited adverse events were collected pre-vaccination, and systemic and local solicited adverse events were collected 30 minutes post-vaccination and then daily for 7 days after each vaccination and graded on a scale of 0 (absent), 1 (mild), 2 (moderate) and 3 (severe). Systemic events include: fatigue, headache, myalgia, arthralgia, nausea, chills and fever. Local events include: pain at injection site, erythema, and induration.

The proportion of subjects reporting at least one solicited adverse event will be summarized for each solicited adverse event, any systemic symptom, any local symptom, and any symptoms. The 95% CI calculated using Clopper-Pearson methodology from a binomial distribution (SAS Proc Freq with a binomial option) will be presented (Table 144, Table 145, and Table 146).

For each systemic and local event, any systemic event, any local event, and any solicited event, the maximum severity over 7 days after each vaccination will be summarized for the Safety population. The number and percentage of subjects reporting each event will be summarized by the maximum severity and treatment group, separately for each vaccination and over all vaccinations (Table 147, Table 148, Table 149, Table 150, Table 151, and Table 152). For each event the denominator is the number of subjects with non-missing data for the specific event.

The number of subjects reporting a solicited adverse event will be summarized for each day post vaccination for each vaccination and for all vaccinations combined both in a summary table starting at Table 153 and ending at Table 212 and graphically in a bar chart (Figure 122, Figure 123, Figure 124, Figure 125, Figure 126, and Figure 127).

The mean, standard deviation, median, minimum and maximum duration of solicited events will be summarized (Table 213, Table 214, Table 215).

Day of solicited symptom onset will be summarized graphically (starting at Figure 128 and ending at Figure 139).

Solicited adverse events by subject will be presented in listings (Listing 10 and Listing 11) and graphically (starting at Figure 140 and ending at Figure 175).

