			95% CI			
		TNF	n			
			Mean			
			95% CI			
Note: N=Number of Subjects. n=Number of subjects with results available at time point. NE=Not Estimable						

Tables with Similar Format:

Table 109. Mean Percentages of CD8 T Cells Expressing Cytokines with 95% CI – Age 18-55, Per Protocol Population*

Table 110. Mean Percentages of CD8 T Cells Expressing Cytokines with 95% CI – Age 56-70, mITT Population

Table 111. Mean Percentages of CD8 T Cells Expressing Cytokines with 95% CI – Age 56-70, Per Protocol Population*

Table 112. Mean Percentages of CD8 T Cells Expressing Cytokines with 95% CI – Age ≥71, mITT Population

Table 113. Mean Percentages of CD8 T Cells Expressing Cytokines with 95% CI – Age ≥71, Per Protocol Population*

Table 114. Serum IgG ELISA Geometric Mean Fold Rise (GMFR) and 4-Fold Rise Results by Time Point and Treatment Group - S-2P – Age 18-55, mITT Population

Time Point	Statistic	25 µg mRNA-1273 18-55 years (N=X)	50 µg mRNA-1273 18-55 years (N=X)	100 µg mRNA-1273 18-55 years (N=X)	250 µg mRNA-1273 18-55 years (N=X)	18-55 years (N=X)
Day 15 (14 Days Post Vaccination 1)	n					
	GMFR ^a					
	95% CI					
	4-Fold Rise ^b					
Day 29 Post Vaccination 1 (Pre-Vaccination 2)	n					
	GMFR ^a					
	95% CI					
	4-Fold Rise ^b					
Day 36 Post Vaccination 1 (7 Days Post Vaccination 2)	n					
	GMFR ^a					
	95% CI					
	4-Fold Rise ^b					
Day 43 Post Vaccination 1 (14 Days Post Vaccination 2)	n					
	GMFR ^a					
	95% CI					
	4-Fold Rise ^b					
	n					

Time Point	Statistic	25 µg mRNA-1273 18-55 years (N=X)	50 µg mRNA-1273 18-55 years (N=X)	100 µg mRNA-1273 18-55 years (N=X)	250 µg mRNA-1273 18-55 years (N=X)	18-55 years (N=X)
Day 57 Post Vaccination 1 (28 Days Post Vaccination 2)	GMFR ^a					
	95% CI					
	4-Fold Rise ^b					
	95% CI					
Day 119 Post Vaccination 1 (90 Days Post Vaccination 2)	n					
	GMFR ^a					
	95% CI					
	4-Fold Rise ^b					
	95% CI					

Note: N=Number of Subjects.

Note: n=number of subjects with baseline and data at corresponding visit.

^aGMFR represents the geometric mean fold rise in Endpoint Titer compared to pre-dose 1

^b4-Fold Rise represents the percentage of subjects with at least a 4-Fold Rise in Endpoint Titer compared to pre-dose 1

Tables with Similar Format:

Table 115. Serum IgG ELISA Geometric Mean Fold Rise (GMFR) and 4-Fold Rise Results by Time Point and Treatment Group - S-2P – Age 18-55, Per Protocol Population*

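### SAP 8.2 and 8.3 put Student's t confidence intervals on seroconversion percentages in cohorts of 10 or 15, giving zero width at 100% or 0% and upper limits above 100% just below full response

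*SAP*

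**What the plan says.** SAP 8.2 (secondary immunogenicity) gives one interval method for a list headed by seroconversion: "Seroconversion rates, GMFR, GMT or Williams mean of the AUC will be presented with their corresponding 95% confidence interval (CI) estimates (using Student's t-distribution"). SAP 8.3 (exploratory) does the same: "Seroconversion rates, GMFR, GMT, and Williams mean of AUC will be presented with their corresponding 95% CI estimates (using Student's t-distribution"). Both sections send the GMFR and seroconversion summaries to Tables 114 to 137.

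The outcome is binary: "Seroconversion is defined as a 4-fold increase in antibody titer over baseline". The footnote to the Table 114 mock-up says that the 4-fold-rise row "represents the percentage of subjects with at least a 4-Fold Rise in Endpoint Titer compared to pre-dose 1". The secondary summaries "will be calculated at Days 1 (GMT only) and 57 by cohort". Cohorts have 15 subjects (18-55 years) or 10 (56-70 and ≥71 years).

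For binary safety outcomes the SAP does something different. Section 9 proposes "dichotomizing into a binary variable (none versus mild, moderate, or severe) and using standard techniques, such as exact confidence intervals (CI"), and section 9.3.1 is more specific: "The 95% CI calculated using Clopper-Pearson methodology from a binomial distribution". Protocol 9.4.3 and 9.4.9 ask for 95% intervals on seroconversion rates but name no method.

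**The concern.** A t interval is suitable for the mean of log titers. Applied to 0/1 data from 10 or 15 subjects, it takes its standard error from the observed proportion alone. That standard error falls to zero when every subject, or no subject, responds. The interval is also symmetric, so near 100% it runs past the end of the scale.

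Seroconversion is a named secondary endpoint, with Day 57 as the secondary timepoint. An upper limit of 112.6% is visibly wrong. An interval of 100% to 100% is the more serious case, because it can pass for a finished result while claiming certainty that 10 subjects cannot provide.

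**Working it through.** The documents contain no numerical seroconversion interval, so there is no planned figure to reproduce.

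**Inputs.** n = 10 or 15 (SAP section 5 and Table 1). The level is 95%, taken as two-sided because the SAP does not say. The t quantiles are t(0.975, 9) = 2.262 and t(0.975, 14) = 2.145.

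**t interval on 0/1 data.** With p = x/n, the sample standard deviation divided by √n equals √[p(1−p)/(n−1)], so the limits are p ± t × √[p(1−p)/(n−1)].

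- 10/10: √(1 × 0/9) = 0, so the interval is 100% to 100%.
- 9/10: √(0.9 × 0.1/9) = 0.100; 2.262 × 0.100 = 0.226; limits 67.4% and 112.6%.
- 14/15: √(0.9333 × 0.0667/14) = 0.0667; 2.145 × 0.0667 = 0.143; limits 79.0% and 107.6%.

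**Exact (Clopper-Pearson) interval.** The lower limit is the 0.025 quantile of Beta(x, n−x+1) and the upper limit is the 0.975 quantile of Beta(x+1, n−x). When x = n the lower limit reduces to 0.025^(1/n): 69.2% for n = 10 and 78.2% for n = 15.

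| Result | Student's t | Clopper-Pearson |
|---|---|---|
| 10/10 | 100% to 100% | 69.2% to 100% |
| 9/10 | 67.4% to 112.6% | 55.5% to 99.7% |
| 0/10 | 0% to 0% | 0% to 30.8% |
| 15/15 | 100% to 100% | 78.2% to 100% |
| 14/15 | 79.0% to 107.6% | 68.1% to 99.8% |
| 13/15 | 67.2% to 106.2% | 59.5% to 98.3% |

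The t upper limit exceeds 100% at 7, 8 and 9 of 10 (104.6%, 110.2%, 112.6%) and at 12, 13 and 14 of 15 (102.9%, 106.2%, 107.6%). It is back inside the scale at 6/10 (96.9%) and 11/15 (98.7%). Dividing by n instead of n−1 does not change the pattern: the upper limits are then 111.5% at 9/10 and 107.1% at 14/15. The pooled age-group columns are affected too, with upper limits of 103.5% at 29/30 and 101.7% at 59/60.

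**Coverage.** Binomial probabilities were summed over all x whose interval contains the true rate. The true rates of 80%, 90% and 95% are assumptions. The chance of a zero-width interval at 100% is (true rate)^n, for example 0.9^10 = 34.9%.

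| n | True rate | t coverage | Exact coverage | Chance of zero width |
|---|---|---|---|---|
| 10 | 80% | 88.6% | 99.4% | 10.7% |
| 10 | 90% | 65.0% | 98.7% | 34.9% |
| 10 | 95% | 40.1% | 98.8% | 59.9% |
| 15 | 80% | 96.1% | 98.2% | 3.5% |
| 15 | 90% | 79.2% | 98.7% | 20.6% |
| 15 | 95% | 53.6% | 99.5% | 46.3% |

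At 90% and above, almost all of the lost coverage comes from the zero-width case. For n = 10 at 90%, 100% − 34.9% = 65.1%, against a computed coverage of 65.0%.

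**The case against.** The best defence is that this is loose drafting and not a chosen method. Later in SAP 8.3, for the neutralization assays, the same parenthesis is attached to geometric means only: ID50 and ID80 "will be summarized by group using the geometric mean and 95% CI (using Student's t-distribution"). In 8.2, the sentence just before the one at issue attaches a log10-scale remark to the same list, and that remark cannot sensibly apply to a percentage. So parentheses in this paragraph do not reliably govern every item. A careful programmer might also carry Clopper-Pearson over from section 9.3.1.

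That is a fair reading of intent, and probably the right one. It does not settle the matter. Section 9.3.1 covers solicited events only, section 9 covers adverse events, and no sentence exempts seroconversion from the t method. Even on the kinder reading, the SAP names no interval method for a secondary endpoint, and the same correcting sentence is needed.

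Other points on that side also stand. Each table cell shows n and individual titers are listed, so a reader could work out the exact limits. At 80% with n = 15, t coverage is adequate. Denominators at Day 57 may fall below 10 or 15, since four subjects missed the second dose (protocol Table 13 footnote). That does not rescue the method: 13/13 and 14/14 also give zero width, against exact lower limits of 75.3% and 76.8%. Finally, Clopper-Pearson is not the only acceptable choice. A Wilson interval would also work, giving 72.2% to 100% at 10/10.

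**Conclusion.** The concern holds. As written, SAP 8.2 and 8.3 prescribe an interval that fails for seroconversion percentages near 100% or 0% in cohorts this small. The zero-width and above-100% results are arithmetic and need no assumption about the true rate. How often they would arise does depend on that rate: the problem is small at 80% and large at 90% or more.

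The consequence is limited. The percentages themselves, GMT and GMFR are unaffected, and so is the primary safety analysis. No hypothesis test, enrolment decision or halting rule uses these intervals. It should be corrected because it misstates the precision of a named secondary endpoint and costs almost nothing to put right.

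**What to change.** In SAP 8.2 and 8.3, limit Student's t to the means computed on the log scale (GMT, GMFR and Williams mean). Add to each section that seroconversion and 4-fold-rise percentages in Tables 114 to 137 carry exact Clopper-Pearson 95% intervals, as in section 9.3.1, and repeat this in the table footnotes.

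The cost is one sentence per section plus the footnote, with no new data and no new tables. While editing, check the mock-ups. In the available text, Table 126 has an interval row under 4-Fold Rise at every visit, but Table 114 shows one only at Days 57 and 119. The missing rows may be an artefact of text extraction.

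All limits will then lie between 0% and 100%, and near 100% they move downward. Intervals become wider at full response and at 14/15, and slightly narrower at 9/10 (44.2 points against 45.2) and 13/15 (38.8 against 39.0).

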8.3. Exploratory Immunogenicity Analyses

Summaries and analysis of immunogenicity data will be presented for the mITT population. If there are protocol deviations which may affect the analysis, a PP analysis may also be performed. If PP population is different than mITT then the PP population will be used in the interim CSR.

Seroconversion is defined as a 4-fold increase in antibody titer over baseline.

Seroconversion rates, GMFR, GMT or Williams mean of AUC for SARS-CoV-2 (S-2P and RBD) as measured by IgG, IgA and IgM ELISA, calculated for specified timepoints by cohort and will be summarized graphically (log₁₀ scale). Seroconversion rates, GMFR, GMT, and Williams mean of AUC will be presented with their corresponding 95% CI estimates (using Student's t-distribution) at each timepoint and overall peak GMT/AUC (starting at Table 24 and ending at Table 47 for GMT/Williams mean and starting at Table 114 and ending at Table 137 for GMFR and seroconversion summaries). AUC is calculated using the trapezoidal method applied to a serial dilution curve. For samples with an AUC of zero at baseline, fold-rise will be

calculated by dividing post-vaccination result by the lowest reported value. Graphical displays will include reverse cumulative distribution plots (Figure 4, Figure 5, Figure 6, Figure 7, Figure 8, Figure 9, Figure 10 and Figure 11), individual titer values over time (starting at Figure 12 and ending at Figure 23), geometric mean over time (Figure 24, Figure 25, Figure 26, Figure 27, Figure 28, Figure 29, Figure 30 and Figure 31) and distributions of responses over time (starting at Figure 48 and ending at Figure 71). Note only endpoint titer values will be reported in the iCSR.

Neutralization assays using SARS-CoV-2 pseudovirus neutralization assay (PsVNA) or a wild-type SARS-CoV-2 plaque reduction neutralization test (PRNT) will be run using serial dilutions. ID₅₀ and ID₈₀ will be calculated for PsVNA data using a 5-parameter logistic regression model. ID₅₀ and ID₈₀ will be summarized by group using the geometric mean and 95% CI (using Student's t-distribution) (starting at Table 48 and ending at Table 59). Table 60, Table 61, Table 62 and Table 63 show the day 43 GM summaries of the PsVNA assay at day 43 of the 614D variant. Similarly, for PRNT data, PRNT₈₀ will be calculated using a 5-parameter logistic model. PRNT₈₀ will be summarized using a geometric mean and 95% CI (Table 64, Table 65, Table 66, Table 67, Table 68 and Table 69). Neutralization endpoints will also be displayed graphically on a log₂ or a log₁₀ scale. Similar methods will be used to summarize all additional neutralization assays performed (nanoluciferase-based live virus high throughput neutralization assay, nLuc HTNA, and 2 versions of a live virus focus-reduction neutralization test, FRNT and FRNT-mNG) (starting at Table 70 and ending at Table 95). Graphical displays for PsVNA will include individual titer values over time (Figure 20, Figure 21, Figure 22, and Figure 23), geometric mean over time (Figure 32, Figure 33, Figure 34, and Figure 35) and distributions of responses over time (starting at Figure 72 and ending at Figure 83). Graphical displays for PRNT, nLuc-HTNA, FRNT and FRNT-mNG will include geometric mean over time (starting and Figure 36 and ending at Figure 47) and distributions of responses over time (starting at Figure 84 and ending at Figure 103).

Individual immunogenicity responses are shown in Listing 8.

Spearman correlation between various binding and neutralization assays will be assessed starting at Figure 104 and ending at Figure 115.

Summaries and analysis of cellular assay data will be presented for the mITT population. If there are protocol deviations which may affect the analysis, a PP analysis may also be performed. If PP population is different than mITT, then the PP population will be used in the interim CSR.

The magnitude, phenotype and percentage of cytokine producing S protein-specific T cells will be summarized at each timepoint by Treatment Group. Mean percentages of CD4 T-cells and 95% confidence will be presented for Th1 and Th2 responses using S1 and S2 peptide pool stimulations starting at Table 96 and ending at Table 107. The Th1 cell types tested will be interferon gamma (IFN- γ), interleukin-2 (IL-2) and tumor necrosis factor alpha (TNF- α). The Th2 cell types tested will be interleukin-13 (IL-13) and interleukin-4 (IL-4). Mean percentages of CD8 T-cells and 95% confidence will be presented using S1 and S2 peptide pool stimulations starting at Table 108 and ending at Table 113. The CD8 cell types tested will be IFN- γ , IL-2 and TNF- α . Distributions of T-cell percentages will be graphically displayed in Figure 116, Figure 117, Figure 118, Figure 119, Figure 120, and Figure 121.

Individual T-cell responses are shown in Listing 9.

